12.3 Statistical Methods

12.3.1 Methods of Data Collection

Structured data elements will be collected remotely through a mobile or web-based platform, by telephone with study personnel, by home visit by study personnel, or (if no other option) by return of written questionnaire by postal mail.

Biospecimen collection will be handled following the RECOVER Adult Standard Collection Workflow Manual of Operating Procedures or RECOVER Adult Local Collection Workflow Manual of Operating Procedures and associated reference materials. Either central or local processing is acceptable if procedures are followed.

Off-protocol clinically obtained samples including cerebrospinal fluid, bronchoalveolar lavage specimens, procedural biopsies, and surgical pathology specimens will be tracked and either transferred from study site biorepository to the central RECOVER biorepository or linked by the patient ID to the institutional RECOVER biorepository for future access.

12.4 Strategies for Study Modifications

This protocol is designed to be pragmatic and flexible in design. We will undertake the following procedures to guide protocol modifications over time:

- 1) The frequency of PASC will be monitored in real-time during the study. If the incidence or prevalence is found to be higher or lower than planned, recruitment strategies will be altered to deliberately undersample/oversample PASC cases.
- 2) Subject response burden will be monitored in real-time during the study. If burden is found to be excessive, it will be reduced by altering the data collection strategy, such as by increasing the assessment interval; reducing the number of data elements collected; increasing the availability of home-based assessments; and/or increasing subject reimbursement.
- 3) Free text responses to interval assessments will be monitored in real-time during the study. If a new symptom or outcome is being reported at a frequency >15% by subjects, the symptom will be added to the data collection tool.
- 4) Data elements may be modified based on ongoing analysis by DRC; data elements that are not informative to PASC definition models may be removed, with substitution by new data elements.

- 5) PASC definition will be revised in an iterative manner based on existing PASC data, medical literature, and feedback from patient representatives, subjects, and the scientific community. Updated PASC definitions may be used to implement a strategy to modify deeper phenotyping.
- 6) Tier 2 and Tier 3 assessments will be evaluated for futility at pre-specified intervals; protocol assessments will be adjusted accordingly and may include elimination of some assessments and introduction of other new assessments.

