Objectives	 Characterize the incidence and prevalence of sequelae of SARS-CoV-2 infection. Characterize the spectrum of clinical symptoms, subclinical organ dysfunction, natural history, and distinct phenotypes identified as sequelae of SARS-CoV-2 infection. Define the biological mechanisms underlying pathogenesis of the sequelae of SARS-CoV-2 infection. 	
Methodology	Ambi-directional longitudinal meta-cohort study (combined retrospective and prospective) with nested case-control studies.	
Endpoint	Primary Endpoints: Presence of candidate PASC symptoms over time (incidence and prevalence). Secondary Endpoints: Biological and recovery trajectories from SARS-CoV-2 infection; organ injury; incident clinical disease.	
Study Duration	Four years	
Subject Duration	Up to four years	

Title	NIH RECOVER: A Multi-site Observational Study of Post-Acute Sequelae of SARS-CoV-2 Infection in Adults	
Population	Infected: Individuals at least 18 years of age meet WHO criteria for suspected, probable or confirmed SARS-CoV-2 infection on or after January 1, 2020.	
	Uninfected: Individuals at least 18 years of age who have never met any of the WHO criteria for suspected, probable or confirmed SARS-CoV-2 infection.	
Number of subjects	12,200 total subjects with SARS-CoV-2 infection and 2,680 total subjects without SARS-CoV-2 infection.	
Statistical Analysis	A flexible study design is proposed to allow modifications to PASC case definition, tiered phenotyping assessments, comparator groups, and/or statistical plan after its initiation to optimize public health impact without undermining validity and integrity of study findings. Modifications in study design may be based on analyses of structured cohort data, unstructured cohort EHR data, and other cohort EHR data.	

2 Key Roles

Principal Investigators Clinical Science Core [name] MS
Helen L. and Martin S. Kimmel Professor of
Advanced Cardiac Therapeutics
Director Heart Failure Programs
NYU Grossman School of Medicine
Leon H. Charney Division of Cardiology
[name]
New York, NY 10016
[contact]

[name]
Professor and Director, Division of Biostatistics
Department of Population Health
NYU Grossman School of Medicine
[name]
New York, NY 10016
[contact]

[name], MHS
Professor, Department of Population Health at
NYU Grossman School of Medicine
Professor, Department of Medicine at NYU
Grossman School of Medicine
Director, Center for Healthcare Innovation and
Delivery Science

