6.3 Recruitment and Retention

6.3.1 Recruitment Strategy and Procedures

Recruitment of people with and without SARS-CoV-2 infection will be stratified to ensure adequate representation by sex and race/ethnicity as described in section 6.2. For patients with SARS-CoV-2 infection recruited during or after infection, priority will be placed on recruiting patients from lists of SARS-CoV-2 infected patients to ensure that (a) potential patients were identified prior to study enrollment to minimize bias associated with self-referral, and (b) enrollment response rates can be generated from known denominators. If lists are large, recruitment can be phased using random sampling and adequate "working of recruitment lists" to maximize generalizability. Attempts will be made to include a diversity of

sites of care (e.g. not only from a post-COVID clinic or only from patients cared for in academic medical centers) and severity of illness (i.e. not only from hospitalized patients). For patients without SARS-CoV-2 infection, patients will be randomly sampled and recruited from known lists of potential study subjects in similar communities, demographics, and sites of care as those being recruited into the SARS-CoV-2 positive cohort. Recruitment will be stratified to match the SARS-CoV-2 positive group in terms of racial/ethnic diversity, index time point, and proportion of patients not hospitalized, hospitalized but not in the intensive care unit, and those hospitalized in the intensive care unit.

For patients enrolled after acute infection, preference should be given to those who have data and/or biospecimens collected before or during the acute phase available to the investigators, though efforts should still be made in such cases to recruit an unbiased sample of such patients (for instance, by oversampling this group for underrepresented minority patients or those in communities not already well-represented in the cohort).

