12.1 Hypotheses to be Tested

The following hypotheses will be addressed in the analytic approach to Aim 1:

- Hypothesis 1a: Clinically meaningful PASC cases and sub-phenotypes will be discernable based on a combination of candidate PASC symptoms, and potentially other clinical features.
- Hypothesis 1b: Cumulative incidence of long-term sequelae differs between SARS-CoV-2 infected and uninfected individuals, overall and stratified by hospitalization.
- Hypothesis 1c: Incidence rate of long-term sequelae differs between SARS-CoV-2 infected and uninfected individuals, overall and stratified by hospitalization
- Hypothesis 1d: The point prevalence of long-term sequelae differs between SARS-CoV-2 infected and uninfected individuals, overall and stratified by hospitalization.
- Hypothesis 1e: The severity of long-term sequelae differs between SARS-CoV-2 infected and uninfected individuals, overall and stratified by hospitalization.

The following hypotheses will be addressed in the analytic approach to Aim 2:

- Hypothesis 2a: The risk of PASC among infected individuals will vary by: demographic and clinical characteristics, vaccine status at the time of infection, severity of disease (including hospitalization and admittance to ICU), drug exposures, pregnancy during acute infection and calendar time.
- Hypothesis 2b: The rate of recovery from PASC among individuals with PASC will vary by: (i)
 demographic and clinical characteristics and vaccine status at the time of infection, and (ii) severity
 of disease (including hospitalization and admittance to ICU), drug exposures, and pregnancy during
 acute infection.

The following hypotheses will be addressed in the analytic approach to Aim 3:

- Hypothesis 3a: PASC and PASC sub-phenotypes will be associated with concurrent and subsequent abnormal laboratory results and other clinical and subclinical features.
- Hypothesis 3b: The association between PASC and PASC sub-phenotypes with concurrent and subsequent abnormal laboratory results and other clinical and sub-clinical features will be modified by demographic factors, including sex, age and race/ethnicity.
- Hypothesis 3c: Recovery from PASC will be associated with laboratory results and other clinical and subclinical features.
- Hypothesis 3d: The association between SARS-CoV-2 infection and PASC and PASC subphenotypes will be mediated by abnormal laboratory results and other clinical and sub-clinical features.

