12.2 Sample Size Determination

The following factors were considered in determining the sample size

- Expected frequency of PASC in the SARS-CoV-2 infected population. Population estimates from studies with selection bias currently range from 25-70%; we used 25% as a conservative estimate.
- The desire for the cohort distribution to include a diverse population, with overrepresentation from non-Hispanic Black, Hispanic and Asian populations relative to general population prevalence to account for a higher rate of SARS-CoV-2 infection and PASC in these populations
- The desire to be able to perform subgroup analyses based on characteristics such as age, sex, race/ethnicity, pregnancy, vaccination status and combinations thereof.

Table 7 shows minimal detectable effect sizes for the key study questions both for the full study sample (Tier 1 N=14,880; Tier 2 N=4,464 and Tier 3 N=2,976) and for subgroups of 25% thereof. These sample sizes for Tier 2 and Tier 3 assume that 25% of infected subjects will have abnormal symptoms. It is further assumed that all infected subjects with abnormal symptoms will progress to Tier 2 (N=3,050) and 5.6% of infected subjects without symptoms will progress to Tier 2 (N=512). Among uninfected subjects, 26.8% (N=718) will progress to Tier 2. 68% of infected subjects with abnormal symptoms will progress to Tier 3, and 3.8% of infected subjects without symptoms will progress to Tier 3. Among uninfected subjects, 18.2% will progress to Tier 3. The infected cohort is expected to include 1,867 pregnant individuals and the uninfected cohort is expected to include 583 pregnant individuals.

Table 7: Sample size calculations

					Min detectable ES*	
Tier	Comparison groups		Effect of interest	Assumptions	Full sample	25% subgroup (e.g. inpatients, Hispanic individuals, etc.)
1	Infected	Uninfected	Difference in risk of PASC between infected and uninfected	Risk of PASC in infected: 25%	3.50%	6.80%
1	Infected w/ RF	Infected w/out RF	Risk difference for PASC in infected with RF vs. without RF	Prevalence of RF: 20%, risk of PASC in infected, RF+: 30%	3.90%	7.60%
1	Pregnant infected	Non- pregnant infected	Risk difference for PASC in pregnant infected versus non- pregnant infected	Risk of PASC in non-pregnant infected: 25%	4.10%	8.00%
1	PASC+ w/ RF	PASC+ w/out RF	Difference in proportion who recover from PASC for those with and without a risk factor	Prevalence of RF: 20%, probability of recovery in PASC+ w/out RF: 0.50	8.70%	17.20%

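### Section 12.4 item 1 ties recruitment of PASC cases to the observed PASC frequency, which is itself the primary endpoint, and does not keep case-targeted recruits out of the frequency estimates

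*Protocol*

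**What the plan says.** Section 12.4 lists procedures to guide modification of the protocol over time. Item 1 opens with "The frequency of PASC will be monitored in real-time during the study" and continues: "If the incidence or prevalence is found to be higher or lower than planned, recruitment strategies will be altered to deliberately undersample/oversample PASC cases". The wording is mandatory and works in both directions. It gives no trigger size, no cap, and no requirement to record when a change began or who was recruited under it. It concerns recruitment into the cohort; adaptation of Tier 2 and Tier 3 testing is handled separately, in item 6 and in section 6.1.

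The quantity being monitored is also the main quantity being estimated. The first objective in the Protocol Summary is "Characterize the incidence and prevalence of sequelae of SARS-CoV-2 infection", and the primary endpoint there is the presence of candidate PASC symptoms over time, as incidence and prevalence. Hypotheses 1b and 1c in section 12.1 concern cumulative incidence and incidence rate. Hypothesis 1d reads: "The point prevalence of long-term sequelae differs between SARS-CoV-2 infected and uninfected individuals, overall and stratified by hospitalization".

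For the expected PASC frequency among infected people, section 12.2 says "we used 25% as a conservative estimate". Section 6.3.1 gives priority to recruiting infected people from lists, partly so that "potential patients were identified prior to study enrollment to minimize bias associated with self-referral".

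**The concern.** Item 1 samples on the outcome, in response to the observed frequency of the outcome. That is harmless, and often efficient, when PASC-positive and PASC-negative people are compared. It is not harmless when the outcome's frequency is the estimand.

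Selection on PASC status is feasible. Section 7.1 admits infected people up to 36 months after infection, and Table 3 has a post-acute infected category. The Acute Infected (Reinfected) category is also open to it, because the index date there is the first infection and such people may already have PASC.

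Two things are at stake. First, read in order, the rule undersamples cases when the frequency is above plan and oversamples them when it is below. It therefore draws the crude frequency towards the planning figure, and the cohort could seem to confirm its own assumption. Second, PASC cases are infected, so the rule acts on one side of the infected-versus-uninfected comparison. Stratifying by hospitalization does not remove this.

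**Working it through.** **Inputs from the protocol.** 12,200 infected and 2,680 uninfected (Protocol Summary). Planning PASC risk of 25% in infected (section 12.2 and Table 7, row 1). Minimum detectable infected-uninfected difference of 3.50% in the full sample and 6.80% in a 25% subgroup (Table 7, row 1).

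**Assumptions.** Section 12.4 does not say which figure is meant by plan; 25% is used here. The true source frequency *p*, the share *f* of infected recruits taken under the altered strategy, and the relative sampling odds *k* of a case against a non-case are not in the protocol and are varied.

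**Step 1: reproduce the benchmark.** With a pooled-variance normal approximation, the detectable difference *d* = p1 - p2 satisfies

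d = z(alpha/2) × sqrt[p̄(1-p̄)(1/n1 + 1/n2)] + z(beta) × sqrt[p1(1-p1)/n1 + p2(1-p2)/n2].

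Taking n1 = 12,200, n2 = 2,680, p1 = 0.25, two-sided alpha 0.01 and 90% power gives *d* = 3.49%. With one quarter of each group (3,050 and 670) it gives 6.84%. Both agree with Table 7. The protocol does not state alpha or power; this setting is inferred because it fits. Two-sided alpha 0.05 gives 2.55% / 5.03% at 80% power and 2.94% / 5.76% at 90%, which do not fit.

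**Step 2: the rule used to the full.** If recruitment restores 25% exactly, the crude frequency reads 25% whatever the source frequency. When it applies to all infected recruits, the odds required are k = [0.25/0.75] / [p/(1-p)].

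- p = 15%: k = 0.3333 / 0.1765 = 1.89; shift 25 - 15 = +10 points.
- p = 40%: k = 0.3333 / 0.6667 = 0.50; shift 25 - 40 = -15 points.

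**Step 3: the rule used in part.** The crude frequency is (1-f) × p + f × kp/(kp + 1 - p). Only combinations in the direction the rule would push are shown.

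| True p | f | k | Crude frequency | Shift (points) |
|---|---|---|---|---|
| 10% | 0.25 | 2 | 12.0% | +2.0 |
| 10% | 0.25 | 3 | 13.8% | +3.8 |
| 10% | 0.50 | 2 | 14.1% | +4.1 |
| 10% | 0.50 | 3 | 17.5% | +7.5 |
| 15% | 0.25 | 2 | 17.8% | +2.8 |
| 15% | 0.25 | 3 | 19.9% | +4.9 |
| 15% | 0.50 | 2 | 20.5% | +5.5 |
| 15% | 0.50 | 3 | 24.8% | +9.8 |
| 40% | 0.25 | 0.5 | 36.3% | -3.7 |
| 40% | 0.50 | 0.5 | 32.5% | -7.5 |

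Eight of these ten shifts exceed 3.5 points in size; the two mildest do not.

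**Step 4: effect on the comparison.** If uninfected recruitment is unchanged, the crude risk difference is the infected frequency minus an unaffected number, so each shift passes into it one for one.

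**The case against.** Several objections have force.

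*Case enrichment has a purpose.* The design includes nested case-control studies. The PASC-positive comparisons and the recovery question (hypothesis 2b and the recovery row of Table 7) need case numbers. A reader might infer that item 1 should simply be deleted because section 6.1 already lets the Tier 2/3 fractions move. The protocol does not support that. Section 12.2 already assumes that every symptomatic infected participant goes to Tier 2 (3,050). At a true frequency of 15%, 12,200 infected people would yield 0.15 × 12,200 = 1,830, and a fraction already at 100% cannot make up the difference. This objection stands against deletion, but not against separating the two uses.

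*The SAP may deal with it.* Section 12.5 defers the analysis to the SAP, which is not at hand, and weights or a restricted analysis set may be specified there. The point is therefore not that weighting is missing. It is that a stated recruitment rule conflicts with the endpoint and does not require recording of what any correction would need. Section 6.3.1 also permits social media and mass advertising, for which sampling fractions would be hard to know.

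*Section 6.3.1 sets a priority, not a prohibition.* That is correct. Item 1 pulls against its aim but does not breach a rule.

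*There is oversight.* Amendments need IRB approval and the OSMB reviews recruitment. Neither removes the bias. The Protocol Summary's statement that modifications should not undermine validity is an intention without a mechanism.

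**Conclusion.** The concern holds for pooled, unweighted incidence, prevalence and infected-uninfected differences. If the rule were used to the full, the distortion would be +10 points at a true 15% or -15 points at a true 40%; under the partial-use assumptions above it runs from -7.5 to +9.8 points. All of this rests on assumed *p*, *f* and *k*, and on 25% being the planned figure.

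Three stronger readings are not supported:

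- A reader might start at a true 25% and apply k = 0.5 or 3 to all recruits, obtaining 14.3% or 50%. At 25% the frequency is on plan and the rule does not fire; when it fires, it moves the crude figure towards plan, not away.
- A reader might treat every acute enrollee as safe from selection. Acute Infected (Reinfected) participants are not.
- A reader might conclude that the study's frequency estimates are already biased. Nothing in the protocol shows that the rule has been used, and participants enrolled at first infection or while uninfected cannot have been chosen on later PASC status.

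**What to change.** Amend section 12.4, item 1, as follows:

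1. Allow case-targeted recruitment only to supply PASC-positive numbers for the PASC-positive versus PASC-negative, recovery and Tier 2/3 analyses.
2. Record the start date of each change in recruitment and flag every participant recruited under it.
3. Exclude flagged participants from the incidence, prevalence and infected-versus-uninfected estimates (1b to 1d) and from the absolute PASC risks in 2a.
4. As a sensitivity analysis, repeat 1b to 1d in those who could not have been selected on PASC status: Acute Infected (First Infection), Acute Uninfected, and participants enrolled uninfected who later became infected. Leave out Acute Infected (Reinfected). These groups can be identified from Table 3 and section 7.1.1.

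If any case-targeted recruitment has already taken place, the same flag should be applied retrospectively.

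The cost is a short amendment, one added data field, and some loss of precision in the frequency estimates, limited to the flagged recruits. The size of that loss cannot be computed, because the protocol does not say how many people would be recruited this way. Restricting the main analysis to the groups in step 4 would drop all post-acute infected enrollees; the protocol text does not show how many that is, so the restriction is proposed only as a sensitivity analysis.

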12.5 Overview of Analytic Approach to Aims

The complete analytic approach to aims is detailed in the statistical analysis plan, included as a separate attachment.

12.6 Data Management Plan

12.6.1 Data Sources

There are three primary sources of data for the RECOVER cohort studies initiative:

- Prospective observational cohort studies
 - Adult cohort sites
 - o Pediatric cohort sites
 - Pregnancy cohort sites
 - o Autopsy cohort sites
- RECOVER biorepository core
- Data repositories
 - Imaging
 - Pathology
 - o Other

[figure not shown]
12.6.2 Data Categories

RECOVER study data may be divided into two broad categories: structured and unstructured. Structured data can be simple (e.g., surveys/lab tests) or complex (e.g., sleep studies). REDCap will be used to capture structured data electronically. REDCap will include PHI data, which will be used to create the universally unique identifiers (UUIDs), that will enable centralized coordination of biospecimen collection information and other data types.

12.6.2.1 Data Types

RECOVER study data may be divided into at least 12 different operational data types.

- 1. Patient questionnaires (in-person or submitted online; Structured)
- 2. Clinical site historical data (extant data; Structured->Complex)
- 3. Clinical site historical data (extant data; Unstructured)
- 4. EHR repository data (Structured->Complex)
- 5. Lab test results (Structured->Complex)
 - i. Hospital
 - ii. Commercial
 - iii. Home
- 6. RECOVER biorepository inventory data (Biospecimens, slides; Structured->Complex)
- 7. Neuropsychological assessment data (Complex/Structured)
- 8. Functional assessment data (e.g. exercise testing, pulmonary/liver/kidney function; Structured->Complex)
- 9. Digital health/wearable devices and computer software (i.e. fitness trackers, sleep monitors, Zio patch)
- 10. Advanced imaging data (CT and MRI; Unstructured)

- 11. Vaccination status data (Structured)
- 12. Physical exam and physiological testing data (e.g. PFTs, tilt table; Structured->Complex)

12.6.3 Electronic Data Capture (EDC) Methods

A uniform electronic data capture system will be used. Details will be found in the manual of operations.

12.6.4 Source Documents and Access to Source Data/Documents

Source data are all information, original records of clinical findings, observations, or other activities in a study necessary for the reconstruction and evaluation of the study. Source data are contained in source documents. Examples of these original documents, and data records include: hospital records, clinical and office charts, laboratory notes, memoranda, subjects' diaries or evaluation checklists, pharmacy dispensing records, recorded data from automated instruments, copies or transcriptions certified after verification as being accurate and complete, microfiches, photographic negatives, microfilm or magnetic media, x-rays, subject files, and records kept at the pharmacy, at the laboratories, and at medico-technical departments involved in the study.

The study electronic case report form (eCRF) is the primary data collection instrument for the study. However, in some cases paper CRFs may be completed by subjects who cannot access surveys online or prefer paper. Data from these CRFs will be transferred into the eCRF by study staff. All data requested on the eCRF must be recorded. All missing data must be explained. If a space on the CRF is left blank because the procedure was not done or the question was not asked, insert "N/D." If the item is not applicable to the individual case, insert "N/A." Records will be retained of the date and time of any changes to data entered after initial completion.

Access to study records will be limited to IRB-approved members of the study team. The investigator will permit study-related monitoring, audits, and inspections by the IRB/EC, the sponsor, government regulatory bodies, and University compliance and quality assurance groups of all study related documents (e.g. source documents, regulatory documents, data collection instruments, study data etc.). The investigator will ensure the capability for inspections of applicable study-related facilities (e.g. pharmacy, diagnostic laboratory, etc.).

Participation as an investigator in this study implies acceptance of potential inspection by government regulatory authorities and applicable University compliance and quality assurance offices.

13 Ethics/Protections of Human Subjects

